6.6. Followup visits

- 48 weeks, 96 weeks, 144 weeks, and 192 weeks visits
 - Followup medical history (medication changes/additions, key events or interventions/surgeries/hospital admissions, new diagnoses of comorbidities, complications of liver disease [variceal bleeding, ascites, edema, hepatic encephalopathy], liver cancer, other cancer, diabetes, angina, myocardial infarction, and stroke)
 - Liver symptom questionnaire
 - Physical examination
 - Laboratory data (hematology, glucose and insulin, clinical chemistry, liver panel, HbA1c, lipid profile)
 - Interim drinking history (age 8 or older; included in Followup medical history)
 - Food questionnaire
 - Activity questionnaire
 - Quality of life questionnaire
 - Serum specimen for banking and substudies
 - Documentation of any additional liver biopsies performed as part of standard of care

6.7. Database contents

Baseline medical history. The NAFLD Database forms will capture whether the patient was ever diagnosed with NAFLD, dates of biopsies, abbreviated weight history, family history (siblings and patients; particularly of obesity and liver disease), demographic history, past medical/surgical events and illness history (including diabetes, gestational diabetes, hypertension, lipodystrophy, polycystic ovarian syndrome) and other associated co-morbid conditions including previously diagnosed lipid and metabolic disease-related conditions (hypercholesterolemia, hypertriglyceridemia, diabetes mellitus), and all diagnoses related to previous liver disease as well as other diagnoses of major organ systems including cardiac disease, renal disease, endocrine disease, hypertension, gout or other arthropathies, disturbances of vision, peripheral neuropathy, myopathy, pancreatitis, and cholelithiasis.

Baseline medication history. Database forms will capture all prescription medications taken within 6 months prior to entry. These should include medications taken for the treatment of liver disease, diabetes, hypertension, and hyperlipidemia, hormone preparations, aspirin, acetaminophen, NSAIDs, thiazolidinediones, metformin, ursodiol, orlistat, vitamin E, corticosteroids, valproate, methotrexate, diuretics, statins, and fibrates. Database forms will also include information on use of alternative therapies, antioxidants, vitamins, and/or other dietary supplements including vitamins, milk thistle, N-acetyl-cysteine, zinc picolinate, α -lipoic acid, dichloroacetate, coenzyme Q, betaine and carnitine/acyl carnitine. Any known medication allergies will be documented.

Followup medical history. Followup health history will include data on medication changes/additions; key events or interventions/surgeries/hospital admissions; new diagnoses of

6.7. Database contents

comorbidities; complications of liver disease [variceal bleeding, ascites, edema, hepatic encephalopathy], liver cancer, other cancer, diabetes, angina, myocardial infarction, and stroke.

Liver symptom questionnaire. Current symptoms to be queried at screening and each annual followup visit include nausea, abdominal pain/distention, fatigue, insomnia, frequent waking at night, daytime somnolence, pruritus, and muscle cramps.

Physical examination. Initial exam (s1) will include: Vital Signs [temperature, pulse, blood pressure], Anthropometrics: [height, weight (without shoes or heavy clothing), waist (at umbilicus), triceps skinfold, middle upper arm circumference, and hip circumference measurements]; General Signs [lipodystrophic body habitus, muscle wasting, acanthosis nigricans, clubbing, strabismus, ophthalmoplegia, and nystagmus]; and Liver signs [jaundice, spider angiomas, palmar erythema, hepatomegaly, splenomegaly, asterixis,]; Tanner stage (patients age 17 or younger who have not reached full maturity in all Tanner assessments).

Focused physical examination. To include: Vital signs; Anthropometrics; Focused liver signs: [presence or absence of edema, ascites, hepatomegaly, splenomegaly, asterixis].

Alcohol consumption. The objectives of the alcohol use data collection is to (a) estimate both recent and lifetime quantity of alcohol ingestion and (b) assess the effect of alcohol previously consumed on baseline histology. The AUDIT questionnaire (age 8 and older) and Skinner Lifetime Drinking history (age 18 and older) will be administered at baseline; an interim drinking history will be obtained at each followup visit as part of the Followup medical history. The AUDIT is a 10-item questionnaire with a simple scoring scale (estimated time for completion: 2 minutes). The Skinner Lifetime Drinking history is a more detailed questionnaire and may take 15-30 minutes depending upon the level of alcohol consumption.

Nutrition. The objectives of the nutrition data collection are to aid in studies that examine the relationship between energy and macro- and micronutrient intake and hepatic histology in patients with NAFLD. Patients age 18 or older will complete the Block Food Questionnaire. This is a detailed questionnaire likely to take 30-40 minutes to complete. It estimates food frequency and quantity over the preceding 12-month period. Patients age 2 to 17 (or their parents) will complete the Block Brief Food Questionnaire. Food questionnaires will be completed at screening and at annual followup visits. Patients will complete the age appropriate questionnaire, regardless of which questionnaire was completed at previous visits.

Physical activity. The objective of the activity data collection component is to evaluate any correlations between level of activity and disease or mechanisms behind the disease. Patients age 18 or older will complete the Physical Activity Questionnaire; patients age 8 to 17 will complete the Modifiable Activity Questionnaire. Patients age 7 or younger will not complete an activity questionnaire.

6.7. Database contents

Quality of life. The objective of the quality of life data collection component is to evaluate any correlations between self-reported quality of life and disease severity. Patients age 18 or older will complete the Modified SF-36, which is estimated to require 5 minutes to complete. Patients age 5-7 and 8 to 12 will complete the age-appropriate child version of the Pediatric Quality of Life questionnaire, patients age 13-17 will complete the adolescent version of the Pediatric Quality of Life questionnaire, and parents will complete a quality of life questionnaire on their children, including toddlers age 2-4. Patients age 4 or younger will not complete a quality of life questionnaire.

Laboratory items. All laboratory items listed may be obtained as archival material from the patient's chart or should be collected as part of the standard of care. Maximum acceptable intervals between the date of collection of laboratory items and Database registration (date of s1) will be specified on the data collection form. The draw date of the laboratory test must be recorded on the data form. In the case of tests marked [‡], the lower and upper limits of the normal range will be entered into the data collection form.

Hematology: Hemoglobin, hematocrit, white blood cell count (WBC), platelet count.

Clinical chemistry and HbA1c: Creatinine, total protein, sodium, potassium, chloride, bicarbonate, calcium, phosphate, BUN, uric acid, and HbA1c.

Liver panel: Total bilirubin, aspartate aminotransferase (AST)‡, alanine aminotransferase (ALT)‡, alkaline phosphatase‡, gamma glutamyltransferase (GGT), albumin, prothrombin time (PT), and INR.

Screening etiologic tests: Hepatitis B surface antigen, hepatitis B core antibody, hepatitis B surface antibody, and hepatitis C antibody.

Serum iron, total iron binding capacity, ferritin, and hepatic iron index.

Ceruloplasmin (obtain if age 40 or less at s1), alpha-1-antitrypsin level‡ (plus phenotype if abnormal). An *HFE* gene mutation analysis is indicated if there is an abnormality in an iron overload screening test, a family history of iron overload or hemochromatosis, or histological iron of 3+ or greater.

Autoantibody studies (*ANA*, *ASMA*, *AMA*).

Fasting lipid profile and glucose-insulin levels: Fasting is defined as nothing by mouth except water for at least 12 hours prior to blood draw. Lipid profile will include fasting triglyceride and cholesterol (total, LDL and HDL cholesterol). Note if on lipid medication when lipid profile taken. If in doubt about fasting status, test should be repeated.

The fasting blood glucose and insulin must be estimated from the same blood draw and can be drawn at the same time as the lipid profile.

6.7. Database contents**6.8. Serum, plasma, DNA, and liver tissue for banking**

Fasting serum, plasma, DNA, and stored liver tissue will be banked for NASH CRN substudies or ancillary studies. Blood will be drawn at the second screening visit and yearly thereafter on all patients enrolled in the Database. Standardized methods for serum, plasma, DNA, and liver tissue processing that allow for maximal preservation of banked specimens and storage in designated -70 degrees C freezers will be applied across all clinical centers or at the NASH CRN central repository (see NAFLD Database Standard Operating Procedures I: Clinical Center Operations).

NAFLD Database Protocol

7. Statistical and design considerations

This is a clinicopathologic condition-based database designed primarily to allow the compilation of data and collection of specimens for the purpose of the study of the epidemiology and natural history of NAFLD. The study also aims to recruit patients for participation in randomized, controlled therapeutic trials. The recruitment goal is a database of 1500 patients with NAFLD with at least 48 weeks of follow-up.

The primary and secondary objectives of the NAFLD Database, as specified in Sections 2.1 and 2.2 of the protocol, are intentionally very broad. Since this is the largest and most comprehensive study of NAFLD, it is expected that many, as yet unasked, questions related to the etiology, natural history, diagnosis, treatment, and prevention of NAFLD will be answered.

Addressing the questions that arise in connection with the NAFLD Database will require the full gamut of statistical analysis procedures, from survival analysis to ROC curves. Nearly all questions will require identification of appropriate subgroups of patients from all clinical centers contributing to the NAFLD Database with analyses tailored to the hypothesis or question to be addressed.

This process will be accomplished through formal publication proposals submitted by investigators to the NASH CRN Steering Committee. Each of these proposals must include a justification for the sample size and plan for statistical analysis constructed with the help of the Data Coordinating Center. Each proposal must contain the following information:

- Specification of the primary and secondary outcome variables
- Specification of subgroups of special interest when making treatment comparisons (e.g., males vs. females or ethnic/racial subgroups)
- Specification of baseline covariates or methods to be used to select the covariates for adjustment of treatment comparisons
- Specification of methods for dealing with missing values or lost to follow-up
- Specification of primary and confirmatory analytic methods to be used

Since the NAFLD Database will generate longitudinal data over time, analytic methods must account for, as applicable, time to events, repeated measurements, counts, or other discrete responses. For time to event data, we will use the Cox proportional hazards regression model with covariates tailored to the hypothesis under investigation. For hypotheses involving repeated measurements, events, counts or other discrete responses, we will use either of two approaches: (1) generalized linear models with generalized estimating equations (GEE) with robust variance estimation to account for the clustering; or, (2) multilevel generalized linear mixed models with random coefficients to account for within patient clustering as well as other sources of variations like clinic effects.

NAFLD Database Protocol

8. Human subjects issues

8.1. Overview

The study protocol, consent forms, and data collection forms will be submitted to each clinical center's IRB and to the DCC's IRB. Additionally, each clinical center will submit to their IRB any recruitment materials to be used at their site. A site may not initiate any patient contact about the NAFLD Database until the site has IRB approval for the Database and the DCC has certified the site for initiation of patient activities. All study personnel will have completed training in the Protection of Human Subjects per NIH guidelines. The proposed study anticipates recruiting a significant proportion of racial/ethnic minorities (Black or African American, Hispanics or Latino, Asian, American Indian/Alaska Native, Native Hawaiian or other Pacific Islander) as well as non-Hispanic white subjects. We anticipate that the patients recruited from diverse sources, including community and tertiary referral populations, will capture the entire spectrum of NAFLD.

8.2. Standard of care

All subjects enrolled in the NAFLD Database will receive a standard of care for NAFLD and identified associated medical problems as defined by the NASH CRN Standards of Care Committee (see SOP V: Standards of Care for Adult Patients with Fatty Liver Disorders, and SOP VI: Standards of Care for Pediatric Patients with Fatty Liver Disorders). This will include provision of health care counseling and educational materials at enrollment and on an ongoing basis during followup.

8.3. Institutional Review Board (IRB) approval

A site may not initiate patient activities in the NAFLD Database until the site has IRB approval for the NAFLD Database study. Consent forms must have IRB approval. Sites must provide the DCC with copies of the initial IRB approval notice and subsequent renewals, as well as copies of the IRB approved consent statements.

8.4. Consent

Prototype consents and assents will be prepared for the study. Individual sites may add material but may not delete material thought to be necessary for informed consent. Sites may reformat and reword information to conform to their local requirements. A signed consent form will be obtained from the subject (or parent, legal guardian, or person with power of attorney for subjects who cannot consent for themselves, such as those below the legal age). The subject's assent must also be obtained if he or she is able to understand the nature, significance, and risks associated with the study. The consent form will describe the purpose of the study, the procedures to be followed, and the risks and benefits of participation. A copy of the consent form will be given to the subject, parent, or legal guardian, and this fact will be documented in the subject's record.

8.5. Subject confidentiality

All laboratory specimens, evaluation forms, reports, and other records that are part of the study data collection and entry materials will be identified by coded number only to maintain subject confidentiality. All records will be kept in locked file cabinets with access limited to Database investigators. All computer entry and networking programs will identify patients by patient identification number. Clinical information will not be released without written permission of the subject, except as necessary for monitoring by the IRB or DSMB. Clinical information may be reviewed during site visits, but use of personal identifiers will be avoided. Consent procedures and forms, and the communication, transmission and storage of patient data will comply with individual site IRB and NIH requirements for compliance with The Health Insurance Portability and Accountability Act (HIPAA).

8.6. Adverse event reporting

The NAFLD Database will monitor and report unanticipated or adverse events to ensure patient safety in compliance with 45 CFR Part 46, Subpart A; the “Common Rule”, shared by 17 Departments and Agencies. The Common Rule requires written procedures and policies for ensuring reporting of “unanticipated problems” involving risks to participants, IRBs, appropriate institutional officials, and the Department or Agency Head. Since the definitions and reporting requirements for unanticipated events may differ at each participating site, the Database definitions and procedures for adverse events are designed to satisfy the Common Rule requirements. While the definitions and monitoring procedures apply most directly to clinical trials, all patients in the Database will be monitored for occurrence of adverse events, and any adverse events that occur will be reported as appropriate.

8.6.1. Definitions

Adverse event. An adverse event is any untoward medical occurrence that may present itself during treatment or administration with a pharmaceutical product or clinical procedure and which may or may not have a causal relationship with the treatment. Adverse events include any unanticipated problems involving risks to participants, or breaches of protocol which might entail risk to participants. The term “unanticipated problem” includes both new risks and increased rates of anticipated problems.

Serious adverse event (SAE). A serious adverse event is an adverse event occurring at any time during the study that results in death, life-threatening adverse drug experience, inpatient hospitalization or prolongation of existing hospitalization, a persistent or significant disability/incapacity, or a congenital anomaly/birth defect. Other events may also be considered an SAE if, based on medical judgement, the event jeopardized the patient to the point of requiring medical or surgical intervention to prevent the occurrence of any of the conditions for an SAE listed above.

Unexpected adverse event. An unexpected adverse event is any adverse event with specificity or severity that is not consistent with the risk information in the study protocol, current investigator brochure, or current package insert.

8.6. Adverse event reporting**8.6.2. Monitoring for adverse events**

Adverse events will be recorded on study data forms whether or not they are thought to be associated with the Database participation or prior participation in a NASH CRN study. Adverse events may be discovered during regularly scheduled visits or through unscheduled patient contacts between visits.

8.6.3. Reporting serious adverse events

Serious adverse events must be reported upon discovery at the clinical center. This will involve completing a data form describing the severity and details of the event. The SAE form, together with a memo summarizing the circumstances of event and the current status of the patient, must be faxed to the Data Coordinating Center and to the NIDDK project officer within one working day of the discovery of the SAE. Also within one day, the clinical center must notify the NIDDK and Data Coordinating Center of the SAE by telephone or confirmed e-mail. The NIDDK project officer will work with the Data Coordinating Center to transmit the SAE form and memo to all study centers and to the DSMB.

The DSMB will review each SAE report and provide comments to the NIDDK project officer within one week of receipt of the report. If requested by any member of the DSMB, a teleconference will be scheduled to discuss the SAE and recommend any actions to the NIDDK sponsor.

The clinical center must submit to the NIDDK project officer and to the Data Coordinating Center a follow-up memo within one month of the SAE (and periodic updates if needed) to report the details of the disposition of the SAE. The NIDDK project officer will work with the Data Coordinating Center to distribute the follow-up memo to the clinical center and to the DSMB.

8.6.4. Review of adverse events by the DSMB

Summary data on adverse events will be monitored by the DSMB at its semi-annual meetings or more frequently, as needed. These summaries will include analyses comparing rates of adverse events by clinic, or in other subgroups requested by the DSMB. Where applicable, signs and symptoms associated with the adverse event will be graded as to severity by the clinical site staff as mild, moderate, or severe using the Common Terminology Criteria for Adverse Events⁴⁰.

After each meeting, the DSMB will issue a written summary of its review of the study data, including adverse events, for transmission to the IRBs at each of the study centers. Analyses or listings of adverse events will not be provided to the IRBs; however, adverse events involving unanticipated problems involving risks to participants, or breaches of protocol which might entail risk to participants must be reported to local IRBs as soon as possible after they are discovered. Each participating center is responsible for ensuring that all local IRB requirements for reporting adverse events are met.

10.2. Committees

- Steering Committee
 - Executive Committee
 - Database Committee
 - Measures and Assessments Committee
 - Pathology Committee
 - Standards of Care Committee
 - Pediatric Committee
 - Ancillary Studies Committee
 - Presentations and Publications Committee
 - Pilot and Feasibility Studies Committee
 - Treatment Trial Protocol Committee
 - Data and Safety Monitoring Board
-

10.3. Data collection schedule

	Screening visits		Followup visits:				
	s1	s2/enr	Weeks from enrollment				
			24	48	96	144	192
Consent and HIPAA authorization	X
Baseline medical history	X
Followup medical history (including interim drinking history)	.	.	X	X	X	X	X
Liver symptoms questionnaire	X	.	.	X	X	X	X
Detailed physical examination including Tanner stage (if < age 18)	X	.	.	X	X	X	X
Focused physical examination	.	.	X
Imaging studies of liver*							
CT scan†	.	A	A	A	A	A	A
Ultrasound†	.	A	A	A	A	A	A
MRI†	.	A	A	A	A	A	A
Liver biopsy†	.	A	A	A	A	A	A
Provision of standard of care materials	.	X
Database eligibility confirmation	.	X
Alcohol use questionnaires							
AUDIT (age ≥8)	X
Lifetime drinking history (Skinner; age ≥18)	X
Diet questionnaires							
Block Food Questionnaire (adult)	.	X	.	X	X	X	X
Brief Block Food Questionnaire (age 2-17)	.	X	.	X	X	X	X
Activity questionnaires							
Physical Activity Questionnaire (adult)	.	X	.	X	X	X	X
Modifiable Activity Questionnaire (age 8-17)	.	X	.	X	X	X	X
Quality of life questionnaires							
SF-36 (adult)	.	X	.	X	X	X	X
Pediatric Quality of Life							
Child's form (age 5-7, or age 8-12)	.	X	.	X	X	X	X
Adolescent form (age 13-17)	.	X	.	X	X	X	X
Parent's form (age less than 18)‡	.	X	.	X	X	X	X
Hematology	.	X	.	X	X	X	X
Liver panel	.	X	.	X	X	X	X
Clinical chemistry	.	X	.	X	X	X	X
HbA1c§	.	X	.	X	X	X	X
Lipid profile (fasting)	.	X	.	X	X	X	X
Glucose and insulin levels (fasting)	.	X	.	X	X	X	X
Etiologic tests	X
Specimens for banking¶	.	X	.	X	X	X	X

* At least one imaging study for suspected NAFLD or suspected cryptogenic cirrhosis.

† A = as available

‡ Parents complete the Parent form of the Pediatric Quality of Life questionnaire until the child is age 18 (separate parent versions are used for child or teen patients as appropriate)

§ In established or newly diagnosed diabetes.

¶ Specimens for banking and ancillary studies include: liver tissue, serum, plasma, and DNA.

10.4. Whole blood draw schedule: mL of blood to be drawn at screening and followup visits

Procedure*	Study visit (wk)							Total
	s1	s2	24	48	96	144	192	
Fasting glucose and insulin	.	5	.	5	5	5	5	25
Fasting lipid	.	5	.	5	5	5	5	25
CBC	.	5	.	5	5	5	5	25
Clinical chemistry	.	5	.	5	5	5	5	25
Hepatic panel	.	5	.	5	5	5	5	25
HbA1c	.	5	.	5	5	5	5	25
Plasma: TGF- β	.	5 *	.	5	5	5	5	25
Serum: fibrosis markers	.	10 *	.	10	10	10	10	50
Serum: banking	.	30 *	.	30	30	30	30	150
Genetics	.	20 *	20
Other screening	40	40
Total	40	95	0	75	75	75	75	435

All Database study visits except for first screening visit are fasting visits and need to be scheduled for early morning. Fasting is defined as nothing by mouth except water in the 12 hours prior to blood draw.

*For children younger than 8 years of age, blood draw will be as much as possible per institutional guidelines.

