4.4. Target composition of Database population

Patients with primary NAFLD including selected patients with cryptogenic cirrhosis and patients with secondary NAFLD not directly associated with gastrointestinal surgery/bypass will be enrolled in the Database. Patients with acute syndromes of microvesicular fatty liver disease will not be enrolled. Total patient recruitment into the Database is estimated at approximately 1500 patients (about 200 patients per clinical center). Twenty percent of the patients are expected to have suspected NAFLD, 15% are expected to have cryptogenic cirrhosis, and 65% are expected to have definite NAFLD. Thirty to forty percent are expected to be diabetic (about 550 patients). At least 25% of patients are expected to be in the pediatric age group. Site specific enrollment of patients in the category of “suspected NAFLD” will be monitored by the DCC; there will be a cap on the total patients enrolled in this category set at 20% of the projected total enrollment. Of the patients with cryptogenic cirrhosis, the group enrolled with “suspected cryptogenic cirrhosis” will be similarly monitored to limit the total to 50% of all patients with cryptogenic cirrhosis.

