6.1. Screening, consent, and followup overview

While many of the NAFLD Database patients likely will come from the current patient rosters of the NASH CRN investigators, patients may be referred to the NASH CRN from physicians outside the Network and some patients may refer themselves. Patients considered by the site investigator as likely to be eligible for enrollment in the Database may be consented and screened at a visit that is part of the ongoing clinical care of the patient. Tests may be ordered and billed to insurance to appropriately complete the evaluation of liver disease and general medical condition according to a reasonable standard of care.

Patients who are thought to be eligible will be invited to screen for enrollment in the Database. Screening will take place over two visits. At the initial screening visit, the details of Database participation will be introduced. If the patient is agreeable and is judged to have definite or suspected NAFLD, then he/she may enter the formal screening phase. Screening will include both prospective and retrospective data collection. Prospective data collection will be carried out by completion of forms and questionnaires by patients and by performance of various laboratory tests and clinical procedures on patients. Retrospective data collection will be carried out by review of the patient's medical chart and abstraction of various data elements. Abstracted data may include physical measurements and laboratory test results. Liver biopsies obtained previously will be reread by the local NASH CRN pathologist for inclusion of liver histologic findings in the Database. Liver imaging studies obtained elsewhere will be read for eligibility if a liver biopsy is not available or is inadequate for NASH CRN grading.

The two screening visits may occur on 2 separate calendar days and may occur over a period of up to 120 days. The data collected at these visits and during the retrospective chart review are used to determine eligibility and to establish baseline values.

Consent for screening and HIPAA authorization to disclose protected health information with the NASH CRN must be obtained from the patient prior to initiating any data collection for the NASH CRN; this consent and authorization must be obtained at the start of the initial screening visit. The consent will include consent for initial screening and consent to enroll in the Database, including followup.

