6.1. Screening, consent, and followup overview

- Assent for screening and inclusion of data in the Database (child patient)
- Consent for the collection, storage, and use of blood samples for current and future genetic research (adult patient)
- Consent for the collection, storage, and use of blood samples for current and future genetic research (parent or legal guardian of prospective child patient)
- Assent for the collection, storage and use of blood samples for current and future genetic research (adolescent patient)
- Assent for the collection, storage and use of blood samples for current and future genetic research (child patient)

HIPAA authorization forms will be prepared according to local clinical center IRB requirements and guidelines.

Minimum followup on a patient will be 48 weeks, and maximum followup on a patient will be 192 weeks. Data will be collected during screening (2 visits), 24 weeks after enrollment, 48 weeks after enrollment, and at yearly intervals thereafter (a maximum of 7 visits). Appendix 10.3 displays the consent and data collection schedule for screening and followup.

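### The blood draw schedule defers to institutional guidelines only below age 8, so patients aged 8 to 17 are scheduled for the same volumes as adults whatever their size

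*Protocol*

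**What the plan says.** The table in Protocol section 10.4 gives the "mL of blood to be drawn at screening and followup visits". It has a single column of volumes per visit, with no strata by age or weight. Two notes follow it. One concerns fasting. The other is the only one about children: "For children younger than 8 years of age, blood draw will be as much as possible per institutional guidelines".

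Other sections bear on how much is actually drawn:

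- Section 6.8, on specimen banking: "Blood will be drawn at the second screening visit and yearly thereafter on all patients enrolled in the Database".
- Section 6.6 lists, for the annual visits, only a "Serum specimen for banking and substudies", whereas the 10.4 table also has a 5 mL plasma tube at those visits.
- Section 6.7 lets laboratory results come from the patient's chart, the schedule in 10.3 restricts HbA1c to diabetes, and section 5.3 requires separate consent for DNA.
- Section 6.1, on screening: "The two screening visits may occur on 2 separate calendar days and may occur over a period of up to 120 days". On duration: "Minimum followup on a patient will be 48 weeks, and maximum followup on a patient will be 192 weeks".
- Section 4.4, on the population: "At least 25% of patients are expected to be in the pediatric age group". Entry is open from age 2 (section 5.1).

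**The concern.** The protocol accepts the principle that a child's draw should follow institutional guidelines, but ends it at the eighth birthday and gives no reason. From that age the full schedule applies, although body size between 8 and 17 varies widely. Most of the volume at s2 and at each annual visit is taken for research or the specimen bank, not for the child's care.

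The boundary can also be crossed during the study. Follow-up may last 192 weeks, about 3.7 years (192/52), so a child enrolled at 5, 6 or 7 can turn 8 and lose the allowance at the next annual visit.

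What is at stake is patient protection and consistent conduct. A site whose own limit is below the scheduled volume would have to depart from section 10.4, and sites could resolve that differently. No hypothesis test or estimate depends on it.

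**Working it through.** **Inputs.** Tube volumes come from the table in section 10.4. Clinical tubes are glucose and insulin, lipids, CBC, chemistry, hepatic panel and HbA1c, at 5 mL each. Research and banking tubes are plasma for TGF-β (5 mL), serum for fibrosis markers (10 mL) and banked serum (30 mL). Genetics is 20 mL, at s2 only. Other screening is 40 mL, at s1 only.

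**Reproducing the table's totals.**

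- s2: 6×5 + 5 + 10 + 30 + 20 = 95 mL
- Annual visit: 6×5 + 5 + 10 + 30 = 75 mL
- All visits: 40 + 95 + 0 + 4×75 = 435 mL
- By rows: 6×25 + 25 + 50 + 150 + 20 + 40 = 435 mL

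The table is internally correct.

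**Splitting each visit by purpose.**

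| Visit | Clinical | Research and banking | Genetics | Total |
|---|---|---|---|---|
| s1 | 40 | 0 | 0 | 40 |
| s2 | 30 | 45 | 20 | 95 |
| Annual (each) | 30 | 45 (40 if serum only) | 0 | 75 (70 if serum only) |

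Non-clinical blood at s2 is 45 + 20 = 65 mL, or 45 mL if genetic consent is withheld.

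**What the other provisions remove.** These totals are maxima. Without HbA1c (no diabetes), s2 is 95 − 5 = 90 mL and an annual visit 75 − 5 = 70 mL. Archival results can reduce the clinical 30 mL further. Refusing genetic consent removes 20 mL at s2. None of these touches the 45 mL of research and banking tubes, and section 6.8 has banking blood drawn on all enrolled patients.

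**Research and banking blood over the study** (lower figure without genetics, upper figure with the extra 20 mL).

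| Follow-up | As in 10.4 | Serum only at annual visits |
|---|---|---|
| 48 weeks (s2 + 1 annual) | 45 + 45 = 90; +20 = 110 mL | 45 + 40 = 85; +20 = 105 mL |
| 192 weeks (s2 + 4 annual) | 5×45 = 225; +20 = 245 mL | 45 + 4×40 = 205; +20 = 225 mL |

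These sums describe cumulative burden over up to 192 weeks, not any single draw.

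**s1 and s2 on one day.** Section 6.1 permits this but does not schedule it. The maximum is 40 + 95 = 135 mL, of which 40 + 30 = 70 mL is clinical and may be archival, leaving 65 mL for research, banking and genetics. Section 10.4 sets no combined limit.

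**Scale, for illustration only.** The protocol gives no weights, so those below are assumed.

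| Assumed weight | s2, 95 mL | Annual, 75 mL | s1 + s2, 135 mL |
|---|---|---|---|
| 25 kg | 3.80 mL/kg | 3.00 mL/kg | 5.40 mL/kg |
| 40 kg | 2.38 mL/kg | 1.88 mL/kg | 3.38 mL/kg |
| 80 kg | 1.19 mL/kg | 0.94 mL/kg | 1.69 mL/kg |

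The same tube set is about three times as large relative to body weight at 25 kg as at 80 kg (80/25 = 3.2). The document contains no limit to compare these figures with.

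**Reach.** 0.25 × 1500 = 375 expected pediatric patients as a floor. This includes children under 8, whom the note already covers.

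**The case against.** The strongest reply is that no error is shown. Without weights or a limit, nothing proves that 95 or 75 mL is wrong for any patient aged 8 to 17, and choosing 18 instead of 8 could be called a preference. Age 8 is also the protocol's threshold for AUDIT, the interim drinking history and the activity questionnaire. That explains where the number may come from. It is not a reason why blood volume should stop depending on size at that age.

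A second reply is that the note can be read as relaxing a collection target for the youngest, not as switching institutional rules off at 8. It is true that the protocol nowhere tells a site to exceed its own limits. But on that reading the older child still has the full volume as the target and no stated allowance to fall short of it, so the wording needs the same repair.

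Third, control may lie elsewhere. Section 8.3 states: "A site may not initiate patient activities in the NAFLD Database until the site has IRB approval for the NAFLD Database study". An IRB may impose a limit, and SOPs I and VI, which are not shown, may contain one. This stands, and it is why no unprotected patient is asserted. It does not alter the rule in section 10.4.

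Finally, the largest figures are upper bounds. Same-day screening may be uncommon, since s2 requires fasting and s1 does not, and clinical results may be archival. Both points are accepted; the research and banking tubes remain.

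**Conclusion.** The concern holds as a low-severity point, worth considering because the correction is cheap. Followed as written, section 10.4 schedules patients aged 8 to 17 for the same volumes as adults: at most 95 mL at s2, of which 65 mL is for research, banking or genetics (45 mL without genetics), and at most 75 mL at each annual visit, of which 45 mL is for research or banking (40 mL if serum only). No other section of the protocol extends the institutional-guideline rule past age 8 or sets a weight-based limit.

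The conclusion rests on reading the note as the only exception to the table. It does not claim that any volume is unsafe or breaches a particular limit. The number of patients affected is unknown, because the share aged 8 to 17 among the roughly 375 or more pediatric patients is not stated.

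**What to change.** Replace the note under the table in section 10.4 with:

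> For patients younger than 18 years of age, the volume drawn at any visit, and the combined volume when s1 and s2 fall on the same day, will not exceed institutional guidelines; research and banking tubes are reduced first.

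This is one sentence under one table. The price is somewhat less banked blood from smaller children, which does bear on the specimen bank objective in section 2.1. Adolescents whose institutional limit exceeds the scheduled volume would contribute the full amount as now.
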